9.1.1.2 Derived Pharmacokinetic Parameters

Pharmacokinetic parameters will be calculated by standard non-compartmental analysis according to current working practices and using the currently supported version of WinNonlin. All calculations of non-compartmental parameters will be based on actual sampling times. Pharmacokinetic parameters listed will be determined from the plasma concentration-time data, as data permits.

Part 1:

Parameter	Parameter Description
AUC(0-∞)	Area under the concentration-time curve from time zero (pre-dose) extrapolated to infinite time will be calculated as:
	AUC = AUC(0-last) + C(last) / lambda_z
Cmax	Maximum observed concentration, determined directly from the concentration-time data
tmax	Time of occurrence of Cmax, determined directly from the concentration-time data

Part 2

Parameter	Parameter Description
AUC(0-τ)	Area under the plasma drug concentration-time curve from pre-dose to the end of the dosing interval (where τ = 24 h) (Day 1 and Day 11)
AUC(0-∞)	Area under the concentration-time curve extrapolated to infinity will be calculated as: AUC = AUC(0-last) + C(last) / lambda_z
Cmax	Maximum observed concentration, determined directly from the concentration-time data. (Day 1 and Day 11)
tmax	Time of occurrence of Cmax, determined directly from the concentration-time data (Day 1 and Day 11)
tlag	Lag-time (time delay between drug administration and first observed concentration),

Parameter	Parameter Description
	determined directly from the concentration-time data (Day 1)
tlast	Time of last quantifiable concentration, determined directly from the concentration-time data (Day 11)
t½	Apparent terminal phase half-life, calculated as; t½ = ln2 / lambda_z (Day 11)
Сτ	Observed concentration at the end of the dosing interval, determined directly from the concentration-time data (where τ = 24 h) (Day 1 and Day 11)
Ctrough	Observed pre-dose concentrations on Days 2 to 11, determined directly from the concentration-time data

NOTES:

 C24, Cτ and Ctrough will be extracted from the concentration data by Clinical Statistics group and merged with other calculated PK parameters provided by CPMS.

All the derived parameters described above will be listed. For each of these parameters, except tmax and tlag, the following summary statistics will be calculated for each treatment group: n, arithmetic mean, standard deviation (SD), median, minimum, maximum, geometric mean with associated 90% CI, standard deviation of logarithmically transformed data, and the between-participant CV (%CVb) based on the geometric mean for the loge-transformed PK parameters. For tmax and tlag, median, maximum, minimum, arithmetic mean and standard deviation will be calculated.

9.1.2 Summary Measure

The measures used for the treatment comparisons are the following:

- For part 1; $AUC(0-\infty)$, Cmax, and, for food effect, tmax.
- For part 2; Not applicable.

9.1.3 Population of Interest

The primary pharmacokinetic analyses will be based on the Pharmacokinetic population, unless otherwise specified.

9.1.4 Strategy for Intercurrent (Post-Randomization) Events

Not applicable.

9.1.5 Statistical Analyses / Methods

Details of the planned displays are provided in Appendix 12: List of Data Displays and will be based on GSK Data Standards and statistical principles.

Unless otherwise specified, endpoints / variables defined in Section 9.1.1 will be summarised using descriptive statistics, graphically presented (where appropriate) and listed.

Statistical Methodology Specification

The following pharmacokinetic statistical analyses will only be performed if sufficient data is available (i.e. if participants have well defined plasma profiles).

Part 1A Relative Bioavailability

Endpoint / Variables

AUC(0-∞) and Cmax

Model Specification

AUC(0-∞) and Cmax will be separately analysed using a mixed effects model. The dependent variable will be the log-transformed PK parameters of interest (AUC(0-∞) and Cmax) and the independent variables will include fixed effects for treatment (GSK2838232 200 mg/r tablet or GSK2838232 200 mg/r capsule), sequence and period, and participant (sequence) as a random effect.

Model Checking & Diagnostics

- Model assumptions will be applied, but appropriate adjustments may be made based on the data.
- The Kenward and Roger method for approximating the denominator degrees of freedom and correcting for bias in the estimated variance-covariance of the fixed effects will be used.
- Normality assumptions underlying the model used for analysis will be examined by obtaining a
 normal probability plot of the residuals and a plot of the residuals versus the fitted values (i.e.
 checking the normality assumption and constant variance assumption of the model
 respectively) to gain confidence that the model assumptions are reasonable.
- If there are any departures from the distributional assumptions, alternative models will be explored using appropriate transformed data.

Model Results Presentation

- Geometric least-squares means for each treatment (tablet or capsule), point estimates and associated 90% confidence intervals for the ratios for each parameter will be produced in tabular format. Estimates of within-subject variability (%CVw) will also be provided. %CVw represents a pooled measure of within-subject variability across all treatments.
- Comparative plots of individual PK parameters will be generated by treatment on linear and semi-logarithmic scales.
- Plots of adjusted geometric mean ratio of test to reference treatment together with 90% confidence intervals will be produced.
- Listing of individual PK parameter ratios will be generated.
- Supportive SAS output from statistical analysis will be generated.

Subgroup Analyses

Not applicable

Sensitivity and Supportive Analyses

Not applicable

Part 1 A and 1B Food Effect

Endpoint / Variables

AUC(0-∞) and Cmax

Model Specification

- AUC(0-∞) and Cmax will be separately analysed using a mixed effects model. The dependent variable will be the log-transformed PK parameters of interest (AUC(0-∞) and Cmax) and the independent variables will include a fixed effect for treatment (with or without food) and participant as a random effect.
- To assess the effect of food on GSK2838232 exposure of the tablet formulation (Part 1A and Part 1B)

Model Checking & Diagnostics

- Model assumptions will be applied, but appropriate adjustments may be made based on the data.
- The Kenward and Roger method for approximating the denominator degrees of freedom and correcting for bias in the estimated variance-covariance of the fixed effects will be used.
- Normality assumptions underlying the model used for analysis will be examined by obtaining a
 normal probability plot of the residuals and a plot of the residuals versus the fitted values (i.e.
 checking the normality assumption and constant variance assumption of the model
 respectively) to gain confidence that the model assumptions are reasonable. If there are any
 departures from the distributional assumptions, alternative models will be explored using
 appropriate transformed data.

Model Results Presentation

- The estimated difference and CI obtained on the log scale will be exponentiated to provide an
 estimate of the fed to fasted ratio and its associated 90% CI. Estimates of within-subject
 variability (%CVw) will also be provided. %CVw represents a pooled measure of within-subject
 variability across all treatments.
- Comparative plots of individual PK parameters will be generated by treatment on linear and semi-logarithmic scales.
- Plots of adjusted geometric mean ratio of test to reference treatment together with 90% confidence intervals will be produced.
- Listing of individual PK parameter ratios will be generated.
- Supportive SAS output from statistical analysis will be generated.

Subgroup Analyses

Not applicable

Sensitivity and Supportive Analyses

Not applicable

Endpoint / Variables

tmax

Model Specification

- Non-parametric analysis, using PROC NPAR1WAY will be performed on the original scale PK parameters of interest (tmax). The dependent variable will be the original scale PK parameter of interest (tmax) and the independent variables will be treatment (with or without food).
- SAS code:

```
PROC NPAR1WAY data= data hl ALPHA=0.1;
```

CLASS treatment:

VAR pk:

EXACT hl;

/* where PK parameter pk = tmax*/

ods select HodgesLehmann;

RUN:

Model Checking & Diagnostics

 Model assumptions will be applied, but appropriate adjustments may be made based on the data.

Model Results Presentation

 90% CIs for the estimation of the treatment difference based on the Hodges-Lehman estimator will be produced

Subgroup Analyses

Not applicable

Sensitivity and Supportive Analyses

Not applicable

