4. OBJECTIVES AND ENDPOINTS

Part 1:

Objectives	Endpoints
Primary	
To assess the relative bioavailability of a novel GSK2838232 tablet formulations versus the capsule formulation (Part 1A)	• AUC(0-∞) and Cmax,
To assess the effect of food on GSK2838232 exposure of the tablet formulation (Part 1A and Part 1B)	• AUC(0-∞), Cmax, and tmax
Secondary	
To investigate the safety and tolerability of GSK2838232 following single dose administration as tablets or capsules, with RTV	GSK2838232 safety parameters: AEs; absolute values and changes over time of clinical laboratory evaluations (hematology, clinical chemistry, urinalysis), vital signs, and ECG parameters from pre-dose values
To characterize the PK of GSK2838232 after administration of a novel tablet formulation and capsule formulation with food, and the tablet formulation given without food	• tlag, tmax, t½, tlast, C24, and AUC(0-t)

Part 2:

Objectives	Endpoints		
Primary			
To assess the safety of GSK2838232 administered as non-boosted once-daily doses of a tablet formulation for 11 days	GSK2838232 safety parameters: AEs; absolute values and changes over time of clinical laboratory evaluations (hematology, clinical chemistry, urinalysis), vital signs, and ECG parameters from pre-dose values		
To assess the PK of GSK2838232 administered as non-boosted once-daily doses of a tablet formulation for 11 days	 Day 1 dose: AUC(0-τ), Cmax, Cτ, tmax, tlag Day 11 dose: AUC(0-τ), AUC(0-∞), Cmax, Cτ, tmax, t½, tlast 		

Objectives	Endpoints
Secondary	
To assess time to steady-state of GSK2838232 when administered as non-boosted once-daily doses of a tablet formulation for 11 days	• Pre-dose concentrations on Days 2 to 11
To assess accumulation of GSK2838232 when administered as non-boosted once-daily doses of a tablet formulation for 11 days	• Accumulation ratios: Ro[AUC(0-τ)], R(Cmax), R(Cτ)

t1/2= Apparent terminal phase half-life; tmax= Time of occurrence of Cmax; tlag= Lag-time (time delay between drug administration and first observed concentration above LOQ in plasma); AUC (0-t) = Area under the concentration-time curve from zero up to a definite time t

[figure not shown]

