5.2. Number of Participants

In order to have sufficient evaluable participants for the above mentioned study objectives, it is expected that a sufficient number of participants will be screened in order to enroll a sufficient number of participants for analysis as given below:

Part 1:

It is expected that approximately 16 healthy participants will be enrolled to provide at least 12 evaluable participants through the three study periods (at least 6 participants per treatment). Participants will be evenly assigned to one of the two treatment sequences for the crossover design Part 1A.

Part 2:

It is expected that 10 healthy participants will be enrolled to provide at least 8 evaluable participants through the single study period.

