7.3. Method of Treatment Assignment

Participants will be assigned to study treatment in accordance with the computer generated randomization schedule generated by PAREXEL, using SAS version 9.3 or higher. A separate randomization schedule will be generated for each part of the study. At Screening, potential study participants will be assigned a screening number. Participants will be randomized before the first dose of Study Drug in Part 1A (GSK2838232 tablet or capsule, with RTV) or Part 2 (GSK2838232 tablet or placebo tablet, without RTV) after all screening assessments have been completed and after the Investigator has verified that they are eligible per study inclusion/exclusion criteria. No participant may begin treatment before randomization and assignment of a unique participant identification number.

Each participant scheduled to receive study treatment will receive a participant number when randomized. The randomization number will determine the allocation of treatment sequences (ABC or BAC) for Part 1, and of treatment (GSK2838232 without RTV or placebo) for Part 2. Allocation to treatment for Part 1A or Part 1B (with Part 2 being fixed) will be according to a predetermined random order.

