10.1. Sample Size Determination

Sample sizes are based on prior relative bioavailability studies with GSK2838232 and take into account variability and logistical factors while no formal calculation of power or sample size for Parts 1 or 2 of the study was performed. A sample size of approximately 16 participants for Part 1 and 10 participants for Part 2, considering a drop-out rate of 25%, of the study should be sufficient to provide useful estimates of inter-participant variability for GSK2838232 PK parameters and safety assessments.

Additional participants will be randomized and enrolled to ensure a minimum of 12 evaluable participants for Part 1 (crossover of tablet and capsule) and 8 evaluable participants for Part 2 (6 active: 2 placebo).

Sample size assumptions

For Part 1 of the study: The between-subject variability (%CVb) for AUC(0- ∞), and Cmax parameters from previous studies at different doses were 21% to 47% and 41% to 44%, respectively. Assuming within-subject variability (%CVw) for AUC(0- ∞) and Cmax is 80% of highest between-subject variability (which will be 38% and 35%, respectively), and with the sample size of 12, it is estimated that the precision (i.e., half

width of the 90% confidence interval on the log scale) for the relative bioavailability assessment will be within 31.7% of the point estimate for AUC($0-\infty$), and within 29.0% of the point estimate for Cmax. If the point estimate of the ratio of geometric mean for Cmax is 1, then 90% confidence interval will be approximately (0.78, 1.29).

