10.4. Statistical Analyses

All safety analyses will be performed on the Safety Population.

All PK analyses will be performed on the PK Population.

For assessment of relative bioavailability of tablet versus capsule (AUC($0-\infty$) and Cmax) and effect of food (AUC($0-\infty$), Cmax, and tmax), loge-transformed selected PK parameters (except tmax) will be analyzed using a mixed effects model. The point estimates and their associated 90% confidence interval (CI) will be provided for the

ratios, test/reference (for bioavailability) and fed/fasted (food effect) in PK parameter values on the original scale.

For the parameter tmax, the corresponding non-parametric analysis will be performed on the original scale using CIs for the estimation of the treatment difference.

Steady-state GSK2838232 concentrations will be assessed by estimating the slope of predose concentrations following repeated daily administration. Accumulation of plasma GSK2838232 will be assessed as the ratios of Day 11/Day 1 AUC(0- τ), Cmax, and C τ values.

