5. CONSIDERATIONS FOR DATA ANALYSES AND DATA HANDLING CONVENTIONS

5.1 Study Treatment & Sub-group Display Descriptors

	Treatment Group Descriptions – Part 1			
	RandAll NG	Data Displays for Reporting		
Code	Description	Description	Order in TFL	
C1	GSK2838232 200 mg/r (as 4 x 50 mg) capsule formulation, fed, normal fat (i.e., approximately 30%) meal (reference)	GSK 200 mg/r capsule fed	1	
T1	GSK2838232 200 mg/r (as 2 x 100 mg) tablet formulation, fed, normal fat (i.e., approximately 30%) meal	GSK 200 mg/r tablet fed	2	
T2	GSK2838232 200 mg/r (as 2 x 100 mg) tablet, confirmed from Part 1A, fasted	GSK 200 mg/r tablet fasted	3	

Treatment comparisons will be displayed as follows using the descriptors as specified:

- 1. GSK 200 mg/r tablet fed vs GSK 200 mg/r capsule fed
- 2. GSK 200 mg/r tablet fed vs GSK 200 mg/r tablet fasted

	Treatment Group Descriptions – Part 2			
RandAll NG Data Displays for Reporting		ıg		
Code	Description	Description	Order in TFL	
T3	GSK2838232 500 mg/r (as 5 x 100 mg) tablet formulation, fed, normal fat (i.e., approximately 30%) meal (reference).	GSK 500 mg/r tablet fed	2	
Р	Placebo	Placebo	1	

Treatment comparisons will be displayed as follows using the descriptors as specified:

1. GSK 500 mg/r tablet fed vs Placebo

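### The 90% CI for the tmax food effect uses an independent-samples procedure on paired data, so its stated level does not hold; with moderate positive correlation it is on average too wide

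*SAP*

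**What the plan says.** The Part 1 food-effect objective in Protocol 4 is "To assess the effect of food on GSK2838232 exposure of the tablet formulation (Part 1A and Part 1B"), and its primary endpoints are AUC(0-∞), Cmax and tmax. Protocol 7.3 states: "The randomization number will determine the allocation of treatment sequences (ABC or BAC) for Part 1". B is the tablet fed and C is the same tablet fasted, so both sequences contain both. SAP 5.1 names the comparison as "GSK 200 mg/r tablet fed vs GSK 200 mg/r tablet fasted".

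For AUC(0-∞) and Cmax, SAP 9.1.5 keeps the participant in the model: "independent variables will include a fixed effect for treatment (with or without food) and participant as a random effect". For tmax the same section says "Non-parametric analysis, using PROC NPAR1WAY will be performed on the original scale PK parameters of interest (tmax"). The code given there has CLASS treatment, VAR pk, EXACT hl and ALPHA=0.1. No participant, pair or stratum appears in it, and the text names treatment as the only independent variable.

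Protocol 10.4 says only "For the parameter tmax, the corresponding non-parametric analysis will be performed on the original scale", without stating paired or unpaired. The SAP addendum adds Table 5.12 and SAS listing 73 for this analysis and leaves the method as it was.

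**The concern.** Fed and fasted tmax are two measurements on the same person, but the procedure treats them as coming from two unrelated groups. The exact confidence level of the NPAR1WAY interval is derived under independence, which this design does not provide. With positive correlation, the interval carries between-participant variation that the design was meant to remove.

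This interval is the only inferential result for a primary endpoint, in a study planned for about 12 evaluable participants. What is at stake is the accuracy of its stated confidence level and the precision reported for tmax. The SAP clause allowing adjustments based on the data names no paired method. Sensitivity analyses for tmax are marked not applicable.

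**Working it through.** **Figure to reproduce.** The plan states no precision or sample size for tmax, so there is none.

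**Inputs from the documents.**
- Numbers: "It is expected that approximately 16 healthy participants will be enrolled to provide at least 12 evaluable participants through the three study periods" (Protocol 5.2). Protocol 10.1 sizes the study "considering a drop-out rate of 25" per cent, and 12/(1 − 0.25) = 16. Two cases follow: 12 complete pairs, or 16 fed values with 12 fasted.
- Sampling times: Protocol Table 2, footnote 9.
- Actual sampling times are used (Protocol 10.4.2, SAP 9.1.1.2).

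**Assumptions.** The documents give no tmax mean, SD, shape or fed/fasted correlation ρ.
- Normal case: fasted mean 4 h, fed mean 5 h, SD 1.5 h; ranges over SD 1-2 h and fasted mean 3-5 h.
- Skewed case: lognormal, medians 4 h and 5 h, log SD 0.4 and 0.6.
- Values are snapped to the sampling times, with ±0.03 h jitter for actual times.

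**Why pairing matters.** For n pairs with common variance σ², the mean difference has variance 2σ²(1 − ρ)/n. The independent-samples calculation uses 2σ²/n. The t-interval analogue of the width ratio at n = 12 is

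t(0.95; 22) / [t(0.95; 11) × √(1 − ρ)] = 0.956/√(1 − ρ).

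This gives 1.14, 1.35 and 1.75 at ρ = 0.3, 0.5 and 0.7. It equals 1 at ρ = 1 − 0.956² ≈ 0.09.

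**Exact intervals compared by simulation.** The unpaired interval inverts the rank-sum test over all fed-minus-fasted differences. The paired interval inverts the signed-rank test over the Walsh averages of within-participant differences. The attained levels under each method's own assumptions are close: 91.1% unpaired and 90.8% paired with 12 pairs, and 90.0% unpaired with 16 and 12.

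Normal base case, 12 pairs, 10,000 datasets per setting (ratios taken before rounding):

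| ρ | Mean width, unpaired | Mean width, paired | Ratio | Coverage, unpaired | Coverage, paired |
|---|---|---|---|---|---|
| 0.3 | 2.29 h | 2.03 h | 1.13 | 94% | about 91% |
| 0.5 | 2.26 h | 1.76 h | 1.29 | 96% | about 91% |
| 0.7 | 2.21 h | 1.46 h | 1.51 | 98% | about 91% |

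At ρ = 0 the ratio is 0.98. For continuous normal data at ρ = −0.3, unpaired coverage falls to 86.9%.

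Average unpaired/paired width ratio across shapes:

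| Data | Shape | ρ = 0.3 | ρ = 0.5 | ρ = 0.7 |
|---|---|---|---|---|
| 12 pairs | normal, range | 1.09-1.22 | 1.23-1.36 | 1.43-1.63 |
| 12 pairs | lognormal, log SD 0.4 | 1.06 | 1.20 | 1.42 |
| 12 pairs | lognormal, log SD 0.6 | 1.00 | 1.16 | 1.42 |
| 16 fed, 12 fasted | normal, range | 0.99-1.16 | 1.14-1.31 | 1.36-1.49 |
| 16 fed, 12 fasted | lognormal, log SD 0.4 | 0.95 | 1.09 | 1.29 |
| 16 fed, 12 fasted | lognormal, log SD 0.6 | 0.89 | 1.03 | 1.26 |

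The lognormal rows use 6,000 runs each.

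**Break-even.** The paired interval is on average no narrower below ρ of about 0.1-0.3 with 12 pairs, and below about 0.2-0.5 with 16 fed and 12 fasted. The upper ends belong to skewed data.

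**Point estimate.** With continuous normal data, 12 pairs and ρ = 0.5, the SDs of the two estimates are 0.45 h unpaired and 0.44 h paired. The defect is in the interval, not the estimate.

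**The case against.** The strongest reply is that the loss of precision is assumed and may be small. Protocol 10.1 is the only place that sets within- against between-participant variability. It does so for AUC and Cmax, not tmax, and the within-participant CVs of 38% and 35% are themselves assumed as 80% of between-participant CVs of 47% and 44%.
- If the between-participant CV is the total spread across participants, as SAP 14.5.3 defines it, ρ = 1 − ln(1 + 0.38²)/ln(1 + 0.47²) = 0.32 for AUC, and likewise 0.35 for Cmax.
- If it excludes within-participant variance, ρ is about 0.60.

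On the first reading the gain is modest. With skewed tmax and missing fasted values, the paired interval could even be the wider one. This stands, and it is why the size is given as a range. It does not rescue the stated 90% level, which still rests on an independence that the design contradicts.

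Other points also stand. The analysis is descriptive (SAP 2.4). The choices for Part 1B and Part 2 rest on Part 1A data (SAP 3.1). Individual fed/fasted values remain visible in Table 5.13 and Figure 5.10, although without an interval for the difference. The signed-rank interval assumes roughly symmetric differences and uses only complete pairs. Replacing a planned interval after database lock, in an open-label part, with one expected to be narrower also invites criticism unless both are shown.

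A reader might go further and infer any of the following:
- *The planned interval is always conservative.* It is not: coverage can drop below 90% with negative correlation.
- *The paired interval would be narrower in this trial.* The ratios are averages. For lognormal data (log SD 0.4) on the nominal times with 12 pairs and ρ = 0.5, the unpaired interval was wider in 65% of datasets and narrower in 21%.
- *The food-effect finding for tmax would be wrong.* The documents set no tmax decision rule, and the estimate is unbiased under a location shift.

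**Conclusion.** The concern holds in a limited form. SAP 9.1.5 uses an independent-samples interval on paired data for a primary endpoint, and nothing in the protocol, SAP or addendum corrects it. The mismatch can be read directly from the text and code, and does not depend on any assumption.

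The size does depend on assumptions. Across normal and right-skewed tmax, the average unpaired/paired width ratio at ρ = 0.3, 0.5 and 0.7 is about 1.0-1.2, 1.2-1.4 and 1.4-1.6 with 12 complete pairs. With 16 fed and 12 fasted values it is about 0.9-1.15, 1.03-1.3 and 1.25-1.5. The consequence is a misstated confidence level and, at moderate positive correlation, lost precision on average. It is not a false conclusion.

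Pairing would not separate food from period: C is always given in Period 3, so that confounding remains under either interval.

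**What to change.** In SAP 9.1.5, and for addendum Table 5.12 and listing 73:

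1. For each participant with tmax under both B and C, compute fed minus fasted. Report the one-sample Hodges-Lehmann estimate (median of the Walsh averages) with a 90% CI from the Wilcoxon signed-rank distribution, keeping zero differences in the Walsh averages. State that the interval assumes roughly symmetric differences.
2. Make this the main tmax interval and show the planned NPAR1WAY interval beside it, because the change comes after database lock (SAP addendum, section 1).
3. Report how many participants have only one of the two values.
4. Record the change as a deviation in the clinical study report, as Protocol 10 provides, and say there that food is confounded with Period 3.

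The cost is a few lines of code and a rerun of one table and one listing, with no new data and no change to conduct. The drawback is that participants without both values drop out of this one interval, so it may rest on fewer people than the AUC and Cmax mixed model. It may also be no narrower than the planned one if correlation is low or several fasted values are missing.
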